	Fresh tumor biopsy																																											
	Healthy skin punch biopsy																																											
8.9.1.2	MICROBIOME (optional)																																											
	Nutritional assessment	x																																										
	Stool samples		x																x (and every 12 weeks or at colitis)							(x)																		
POST-STUDY																																												
8.11.4	Survival follow-up (including patients who screen-failed due to ROPRO)																					x																						

Table 2 Pharmacokinetics/Pharmacodynamics for Part I Dose Escalation

Cycle	Day	Scheduled Time (h)	Time-window	PK RO7296682 ^{a, b,} c	ADA RO7296682 ^{a, b,} c	PK Atezolizumab ^{a,} b, c	ADA Atezolizumab ^{a,} b, c	Receptor Occupancy	PD blood FACS	PD Cytokines	Archival sample	Mandatory healthy skin punch biopsy ^e	Optional Biopsy ^f	Blood GEP	TCR VB	Soluble tumor and inflammation markers	Clinical Genotyping (DNA)	RBR (DNA)	RBR (RNA)	IgE/Tryptase ^d
Screening/ Baseline	D-28 to D-1							x				x	x							
Cycle 1	Day 1	Predose - Atezolizumab and RO7296682	-4h	x	x	x	x	x	x	x				x	x	x	x	x		
		EOI - Atezolizumab	+ 30min			x														
		EOI - RO7296682	+ 30min	x					x	x	x									
		EOI+3 - RO7296682	± 30min	x																
	Day 2	24 - RO7296682	± 2h	x																
	Day 4	72 - RO7296682	± 24h	x				x	x	x										
	Day 8	168 - RO7296682	± 48h	x				x	x	x										
Cycle 2	Day 15	336 - RO7296682	± 48h	x				x	x	x										
	Day 1	Predose - Atezolizumab and RO7296682	-4h	x	x	x	x	x	x	x	x									
		EOI - RO7296682	+ 30min	x				x			x									
		Day 8	168 - RO7296682	± 48h					x	x	x		x							
Cycle 3	Day 1	Predose - Atezolizumab and RO7296682	-4h	x	x	x	x	x	x	x	x			x	x	x				
		EOI - RO7296682	+ 30min	x				x												
Cycle 4	Day 1	Predose - Atezolizumab and RO7296682	-4h	x	x	x	x	x	x	x	x									
		EOI - Atezolizumab	+ 30min			x														
		EOI - RO7296682	+ 30min	x				x		x	x									
		EOI+3 - RO7296682	± 30min	x																
	Day 2	24 - RO7296682	± 2h	x																
	Day 4	72 - RO7296682	± 24h	x				x	x	x										
	Day 8	168 - RO7296682	± 48h	x				x	x	x										
	Day 15	336 - RO7296682	± 48h	x				x	x	x										
Cycle 5	Day 1	Predose - Atezolizumab and RO7296682	-4h	x	x	x	x	x				x								
		EOI - RO7296682	+ 30min	x				x												

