4.1.1 Length of the Study

The maximum duration of the study for each participant will be up to 31 months, divided as follows:

- Screening: Days -28 to -1.

- Treatment Period: C1D1 to Month 24 (may be modified if supported by emerging data).
- End of Treatment Visit: 28 (\pm 7) days after last dose
- Safety follow-up: 135 (\pm 30) days after last treatment with RO7296682 in combination with atezolizumab.
- Survival follow-up: 90 (\pm 7) days after the safety follow-up visit; then every 3 months (\pm 14 days) until death, lost to follow-up, or until study closure by the Sponsor, whichever occurs first.

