 - Neutrophil count of $\geq 1.5 \times 10^9$ cells/L (1500/ μ L).
 - Platelet count of $\geq 75 \times 10^9$ /L (75,000/ μ L).
 - Hemoglobin ≥ 9 g/dL (90 g/L, ~ 5.6 mmol/L).
 - Lymphocyte count of $\geq 0.5 \times 10^9$ cells /L (500/ μ L) (borderline lymphocyte values can also be confirmed with manual counts if machine count is below limit).
13. Adequate liver function:
 - Total bilirubin $\leq 1.5 \times$ upper limit of normal (ULN; excluding Gilbert syndrome; see below).
 - AST, ALT, and alkaline phosphatase (ALP) $\leq 2.5 \times$ ULN; with the following exceptions:
 - Participants with documented liver metastases: AST and ALT $\leq 5 \times$ ULN.
 - Participants with documented liver or bone metastases: ALP $\leq 5 \times$ ULN.
 - GGT $> 2.5 \times$ ULN (in case of liver metastases: $\geq 5 \times$ ULN) must be discussed and agreed with the Sponsor.
14. Adequate renal function: serum creatinine $\leq 1.5 \times$ ULN or creatinine clearance by Cockcroft-Gault formula ≥ 50 mL/min for participants in whom, in the Investigator's judgment, serum creatinine levels do not adequately reflect renal function.
15. Additional adequate laboratory parameters obtained prior to the first study treatment (C1D1):
 - Serum albumin ≥ 25 g/L (2.5 g/dL).

- Prothrombin time (PT) and activated partial thromboplastin time (aPTT) $\leq 1.5 \times$ ULN or $< 2 \times$ ULN for participants with hepatocellular carcinoma.

16. Participants on therapeutic anticoagulation must be on a stable anticoagulant regimen.

17. A female participant is eligible to participate if she is not pregnant, not breastfeeding, and at least one of the following conditions applies:

- Not a woman of childbearing potential (WOCBP).
- WOCBP, who:
 - Agree to remain abstinent (refrain from heterosexual intercourse) or use highly effective contraceptive methods that result in a failure rate of $< 1\%$ per year during the treatment period and for at least 4 months after the final dose of RO7296682 and for 5 months after the final dose of atezolizumab, whichever is longer.
 - Examples of contraceptive methods with a failure rate of $< 1\%$ per year include bilateral tubal occlusion, male sterilization, established proper use of hormonal contraceptives that inhibit ovulation, hormone-releasing intrauterine devices (IUDs), and copper IUDs.
- Have a negative pregnancy test (blood) within the 7 days prior to the first study treatment administration.

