Male participants: During the treatment period and for at least 28 days after the last dose of RO7296682, agreement to the following:

- Remain abstinent (refrain from heterosexual intercourse) or use contraceptive measures such as a condom plus an additional contraceptive method that together result in a failure rate of $< 1\%$ per year, with partners who are WOCBP.
- With pregnant female partners, remain abstinent (refrain from heterosexual intercourse) or use contraceptive measures such as a condom to avoid exposing the embryo.
- Refrain from donating sperm during that period.

Specific Inclusion Criteria for Dose Escalation, Part I

18. Participants with histologically confirmed advanced and/or metastatic OvCa, TNBC, HNSCC, NSCLC, MEL, or EsC.

19. In the absence of sufficient archival tissue, a fresh biopsy from a safely accessible site, per Investigator determination and patient consent, will be requested, providing the patient has more than one measurable target lesion.

Note: if fresh biopsy cannot be obtained, please contact the Medical Monitor.

Specific Inclusion Criteria for CPI-resistant Participants, Part II

20. Participants with histologically confirmed advanced and/or metastatic HNSCC, NSCLC or MEL.

21. [REDACTED] positivity established using a validated IHC method and readout (validated laboratory-developed test). For this purpose, the most recent archival sample from a metastatic site (and NOT primary tumor) must be obtained. Please see Section [4.2.1](#) for rationale.

Note: In the absence of sufficient or appropriate archival tissue the immune-phenotype must be confirmed using a fresh tumor biopsy, providing the patient has more than one measurable target lesion. Please refer to inclusion criteria #23.

22. For participants to be defined as acquired CPI-resistant, they must have received prior treatment with approved or investigational anti-PD-1/L1 (Note: prior treatment with anti-CTLA-4 at any time during anti-cancer treatment is prohibited) and meet the following requirements:

- CPI administration as (neo-) adjuvant therapy is not allowed.
- For participants with MEL, no line of chemotherapy is allowed between the most recent PD-1/PD-L1 treatment and study treatment. For participants with HNSCC and NSCLC, a maximum of 1 line of chemotherapy is allowed between the most recent PD-1/PD-L1 treatment and study treatment.

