11. Significant cardiovascular disease (such as New York Heart Association Class II or greater cardiac disease, myocardial infarction, or cerebrovascular accident) within 3 months prior to initiation of study treatment, unstable arrhythmia, or unstable angina.

12. Participants with known active or uncontrolled infection that, in the opinion of the Investigator, could impact patient safety, or reactivation of a latent infection, whether bacterial, viral (including, but not limited to, hepatitis B, hepatitis C and HIV), fungal, mycobacterial (including but not limited to tuberculosis), or other pathogens (excluding fungal infections of nail beds) or any major episode of infection requiring hospitalization or treatment with IV antibiotics (for IV antibiotics, this pertains to completion of last course of antibiotic treatment), or hospitalization for severe pneumonia within 28 days of first drug administration.
13. Positive HIV test at screening.
14. Hepatitis B virus (HBV) or hepatitis C virus (HCV) infection.
15. Vaccination with live vaccines within 28 days prior to C1D1 or anticipation of need for such a vaccine during atezolizumab treatment or within 5 months after the final dose of atezolizumab.
16. Known clinically significant liver disease, including alcoholic hepatitis, cirrhosis, and inherited liver disease.
17. Major surgical procedure or significant traumatic injury within 28 days prior to first RO7296682 and atezolizumab infusion, or anticipation of the need for major surgery before end of treatment period. After major surgery, participant must wait until surgical wounds are fully healed before initiating treatment.
18. Participants with current or history of wound healing complications and/or participants with open wounds until complete resolution.
19. Prior allogeneic stem cell or solid organ transplantation.
20. Dementia or altered mental status that would prohibit informed consent.
21. History of Stevens-Johnson syndrome, toxic epidermal necrolysis, or drug rash with eosinophilia and systemic symptoms.
22. Active or history of autoimmune disease or immune deficiency, including, but not limited to, myasthenia gravis, myositis, systemic lupus erythematosus, rheumatoid arthritis, inflammatory bowel disease, antiphospholipid antibody syndrome, Wegener granulomatosis, Sjögren syndrome, Guillain-Barré syndrome, or multiple sclerosis, with the following exceptions:

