8.3.5 Pregnancy

Female participants of childbearing potential will be instructed to immediately inform the Investigator if they become pregnant during the study or within 4 months after the last dose of RO7296682/atezolizumab.

Male participants will be instructed through the ICF to immediately inform the Investigator if their partner becomes pregnant during the study or within 28 days after the final dose of RO7296682.

If a pregnancy is reported, the Investigator should inform the Sponsor within 24 hours of learning of the pregnancy and should follow the pregnancy reporting process as detailed in [Appendix 5](#).

Abnormal pregnancy outcomes (e.g., spontaneous abortion, fetal death, stillbirth, congenital anomalies, and ectopic pregnancy) are considered SAEs ([Appendix 5](#)).

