8.11.4 Follow-Up Assessments

Safety Follow-Up/End of Study: Participants who complete the treatment or discontinue from the study early, will be asked to return to the clinic 135 (\pm 30) days after the last dose of study drug or last data point determined for an End of Treatment Visit. Assessments should be completed as detailed in the SoA (Section 1.3).

Survival Follow-Up: The sites will provide to the Sponsor (using a designated section of the eCRF) with an update on survival status 90 (\pm 7) days after the Safety Follow-Up visit and then every 3 months (\pm 2 weeks) thereafter up until 24 months post initial treatment (or until study closure) for each participant enrolled in the study. Patients who screen-failed due to the ROPRO score will also be followed up for survival.

After the study completion/early termination visit, AEs should be followed as outlined in Sections 8.3.1 and 8.3.3.

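### Section 8.3.5 asks women to report pregnancies for 4 months after either drug, but inclusion 17 sets 5 months for atezolizumab: a minor mismatch, leaving 0 to about 30 days uncovered depending on when the study is taken to end

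*Combined protocol and SAP*

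**What the plan says.** Section 8.3.5 (Pregnancy) instructs women of childbearing potential to inform the investigator at once if they "become pregnant during the study or within 4 months after the last dose of RO7296682/atezolizumab". One period is given for both drugs.

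Inclusion criterion 17 (Section 5.1) separates the drugs. Contraception lasts at least 4 months after RO7296682 and "for 5 months after the final dose of atezolizumab, whichever is longer".

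For men, Section 5.1 sets the contraception commitment "During the treatment period and for at least 28 days after the last dose of RO7296682", and Section 8.3.5 uses the same 28 days for reporting a partner's pregnancy.

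Appendix 5, Section 4 covers women who become pregnant while participating and refers back to Section 8.3.5. It adds no period of its own.

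Three places bear on when a participant's study ends:
- Section 8.11.4 reads "Safety Follow-Up/End of Study: Participants who complete the treatment or discontinue from the study early, will be asked to return to the clinic 135" days after the last dose, with a window of 30 days either side. Table 1 labels the visit the same way and puts the row "Survival follow-up (including patients who screen-failed due to ROPRO") in its post-study block.
- Section 4.1.1 lists survival follow-up, "until death, lost to follow-up, or until study closure by the Sponsor, whichever occurs first", among the components of each participant's time in the study.
- Section 4.4 defines end of study for the whole trial, by the last participant's last visit or last required data point, whichever is later.

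**The concern.** The contraception period is the protocol's statement of how long exposure might matter to a pregnancy. A pregnancy that begins in the fifth month after atezolizumab lies inside that period but can lie outside the period in which the woman is asked to report it. The sponsor might then learn of it late or not at all. Section 8.3.5 names atezolizumab, so the shorter figure cannot be read as applying to RO7296682 alone, and no section explains why women's reporting should end before women's contraception. The matching periods for men suggest that alignment was intended.

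What is at stake is the completeness of pregnancy reporting in a combination that Section 8.3.9 describes as first-in-human. No statistical quantity is involved.

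**Working it through.** The plan has no calculated figure to reproduce, so the check is date arithmetic.

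**Inputs**
- Reporting period after the last dose: 4 months (Section 8.3.5).
- Contraception period after atezolizumab: 5 months (Section 5.1, criterion 17).
- Safety follow-up visit: day 135 ± 30, so days 105 to 165 (Table 1, Section 8.11.4). Section 4.4 gives ± 35, so days 100 to 170.
- First survival contact: 90 days after the safety visit (Section 4.1.1).
- Assumptions: one month is 30.44 days, and both drugs are last given on the same day.

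**Conversion**
- 4 × 30.44 = 121.8 days (120 to 123 by calendar month).
- 5 × 30.44 = 152.2 days (150 to 153 by calendar month).
- Difference: 30.4 days (28 to 31 by calendar month).

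**Formula.** Let E be the day after the last dose on which *during the study* stops for that woman. Then

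uncovered days = max(0, 152.2 − max(121.8, E)).

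**Narrow reading: the study ends at the safety visit**

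| Safety visit (E) | Uncovered days | Share of 152.2 days |
|---|---|---|
| Day 105 | 152.2 − 121.8 = 30.4 | 20.0% |
| Day 135 | 152.2 − 135 = 17.2 | 11.3% |
| Day 165 | 0 | 0% |

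By calendar month, the day-135 figure is 150 − 135 = 15 to 153 − 135 = 18 days. Any visit up to about day 122 gives the full 30 days, and any visit after about day 152 gives none. The wider Section 4.4 window gives the same range: 30.4 days at day 100 and 0 at day 170.

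**Broad reading: survival follow-up counts, or the trial-wide end of study governs**
- With survival follow-up counted, the first contact after a day-135 visit is at 135 + 90 = day 225, beyond day 152, so uncovered days = 0.
- Under the trial-wide end, a woman whose fifth month falls while the trial is still running also has 0. A gap could remain only for women treated last, for whom the trial may end at or near their own safety visit.

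**Which reading fits better.** Section 4.1.1 gives a maximum of 31 months per participant. Screening (28 days), treatment (24 months) and a day-135 visit come to 28/30.44 + 24 + 135/30.44 = about 29.4 months. Adding 90 days for the first survival contact gives about 32.3. For a participant treated for the full 24 months, the stated maximum fits the narrow reading. The same section nevertheless lists survival follow-up as a component, so the text does not settle the matter.

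**With the period corrected.** Replacing 121.8 by 152.2 in the formula gives 0 uncovered days for every E.

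**The case against.** The strongest reply is that contraception and self-reporting are different obligations. No section says they must be equally long, and a site can follow both without conflict. That is correct, and the men's matching periods are evidence of intent, not a rule. But the protocol offers no reason for the difference.

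The second reply is that *during the study* already covers the fifth month. The only formal end-of-study definition (Section 4.4) is trial-wide, and Section 4.1.1 includes survival follow-up. The narrow reading rests on the visit label, the post-study block in Table 1, and the end of adverse event collection at the safety visit (Section 8.3.1). Both readings are supportable, so any gap is conditional. This reply stands.

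The third reply is that other provisions catch most of what matters:
- Contraception still runs for 5 months.
- The pregnancy-test row in Table 1 appears to reach the end-of-treatment and safety visits, although its columns are broken in the text available.
- The investigator's 24-hour duty to report a known pregnancy has no month limit (Section 8.3.5; Appendix 2, Section 5).
- Spontaneous abortions, toxicity-related induced abortions and congenital anomalies are serious adverse events with no stated month limit (Appendix 5, Sections 5 and 6).
- Related serious events are reportable at any time (Section 8.3.1).

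This also stands in large part. Its limit is that each reporting duty depends on the investigator learning of the event, and a test at day 135 cannot detect a later conception.

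**Conclusion.** The mismatch between 4 and 5 months is certain. The reporting gap is conditional: about 17 days at a day-135 visit and 0 to about 30 days across the visit window if a participant's study ends at the safety visit, and little or no gap if it runs to the trial-wide end or includes survival follow-up. These figures assume 30.44-day months and a common last-dose date. Severity is minor.

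A reader might infer more than the documents support:
- *Every woman has an uncovered month.* This does not follow. Thirty days is the upper end under one reading, and the other reading gives none for most women.
- *Women are told the wrong period.* This cannot be shown, because the consent pages were not available for review.
- *Women who withdraw or are lost, or who finish treatment late, have further gaps.* That requires a participant-level end of study which Section 8.3.5 does not state. Section 7.2 also rules out follow-up after consent is withdrawn, so I attach no figure to these cases.
- *Safety results or dose decisions are affected.* Nothing in the analysis plan depends on this period.

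**What to change.** In Section 8.3.5, keep the reference to pregnancy during the study and change the period that follows it to 4 months after the last RO7296682 dose or 5 months after the last atezolizumab dose, whichever is longer. This matches criterion 17 and leaves no uncovered days under either reading, so the meaning of *during the study* need not be settled for this purpose. Appendix 5 needs no edit on this point because it refers back to Section 8.3.5.

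The cost is one phrase in the protocol, plus the consent text if it repeats the 4-month period. No visits, tests or analyses are added, and the change can go into the next amendment.

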8.3.6 Non-Serious Adverse Events of Special Interest

NSAEIs are required to be reported by the Investigator to the Sponsor immediately (i.e., no more than 24 hours after learning of the event; see [Appendix 2](#) for reporting instructions).

NSAEIs for this study include the following:

- Cases of an elevated ALT or AST in combination with either an elevated bilirubin or clinical jaundice, as defined in [Appendix 3](#).
- Suspected transmission of an infectious agent by the study treatment, defined as:
Any organism, virus, or infectious particle (e.g., prion protein transmitting transmissible spongiform encephalopathy), pathogenic or non-pathogenic, is considered an infectious agent. A transmission of an infectious agent may be suspected from clinical symptoms or laboratory findings that indicate an infection in a participant exposed to a medicinal product. This term applies only when a contamination of the study treatment is suspected.

Atezolizumab-specific NSAEIs:

- Pneumonitis.
- Colitis.
- Endocrinopathies: diabetes mellitus, pancreatitis, adrenal insufficiency, hyperthyroidism, and hypophysitis.
- Hepatitis, including AST or ALT $> 10 \times$ ULN.
- Systemic lupus erythematosus.
- Neurological disorders: Guillain-Barré syndrome, myasthenic syndrome or myasthenia gravis, and meningoencephalitis.
- Events suggestive of hypersensitivity, IRRs, CRS, hemophagocytic lymphohistiocytosis (HLH), and macrophage activation system (MAS).
- Nephritis.
- Myositis.
- Myopathies, including rhabdomyolysis.
- Ocular toxicities (e.g., uveitis, retinitis, optic neuritis).
- Grade ≥ 2 cardiac disorders.
- Vasculitis.
- Autoimmune hemolytic anemia.
- Severe cutaneous reactions (e.g., Stevens-Johnson syndrome, dermatitis bullous, toxic epidermal necrolysis).
- *Myelitis*
- *Facial paresis*

8.3.7 Dose-Limiting Toxicities (Immediately Reportable to the Sponsor)

During the DLT/dose-limiting AE (DLAE) assessment window, AEs identified as DLTs/DLAEs, as defined in Section 4.1.3, are required to be reported by the Investigator to the Sponsor immediately (i.e., no more than 24 hours after learning of the event; see Appendix 2, Section 5 for reporting instructions).

8.3.8 Disease-Related Events and/or Disease-Related Outcomes Not Qualifying as Adverse Events or Serious Adverse Events

Not applicable.

8.3.9 Management of Specific Adverse Events

This section describes the management of specific AEs based on nonclinical toxicology and clinical experience of RO7296682 as well the clinical experience with molecules in the same class. The most common toxicity expected from RO7296682 are IRRs, immune-mediated AEs (imAEs) and skin toxicity. The most common toxicities from CPIs (i.e., atezolizumab) are IRRs and imAEs.

This is the first-in-human evaluation of the combination of RO7296682 and atezolizumab, therefore, the actual risk of combined toxicity is unknown. Nonclinical toxicology studies have not been conducted with the combination of RO7296682 and atezolizumab. Based on nonclinical and/or clinical studies with each molecule as a single agent, as well as on molecules with similar mechanisms of action, there is a potential for overlapping toxicities in participants treated with RO7296682 in combination with atezolizumab. For further details on the identified and potential risks associated with RO7296682 treatment, see the [Investigator's Brochure](#).

Toxicities associated or possibly associated with RO7296682 treatment should be managed according to standard medical practice. Additional tests, such as autoimmune serology or biopsies, should be used to determine a possible immunogenic etiology. For further details on the potential risks associated with RO7296682 treatment, see the [Investigator's Brochure](#).

Measures will be taken to ensure the safety of participants in this study, including the use of stringent inclusion and exclusion criteria and close monitoring of participants during the study. Administration of RO7296682 will be performed in a monitored setting in which there is immediate access to trained personnel and adequate equipment and medicine to manage potentially serious reactions as well as life-threatening conditions including intensive care unit.

Patients with active infection are excluded from study participation. In the setting of a pandemic or epidemic, screening for active infections (including SARS-CoV-2) prior to and during study participation should be considered according to local or institutional

guidelines or guidelines of applicable professional societies (e.g., American Society of Clinical Oncology or European Society for Medical Oncology).

Severe COVID-19 appears to be associated with a CRS involving the inflammatory cytokines IL-6, IL-10, IL-2, and IFN- γ ([Merad and Martin 2020](#)). If a participant develops suspected CRS during the study, a differential diagnosis should include COVID-19, which should be confirmed or refuted through assessment of exposure history, appropriate laboratory testing, and clinical or radiologic evaluations per Investigator judgment. If a diagnosis of COVID-19 is confirmed, the disease should be managed as per local or institutional guidelines.

For events in which management guidelines are not covered in this protocol, participants should be managed as deemed appropriate by the Investigator according to best medical judgment and local medical guidelines. Clinical judgment may be applied, and a risk/benefit consideration may suggest deviating from these guidelines. In this specific case, decisions on study treatments will be taken by the Investigator upon consultation with the Medical Monitor.

Guidelines for management of specific AEs are provided in [Table 11](#), [Table 12](#), and [Appendix 12](#).

